5.5.2 Off-Treatment Data Submission Schedule

Patients will be followed for the resolution of all toxicities considered at least possibly related to ABT-888 occurring while on treatment and for 30 days after the last administration of study drug. Patients will be followed for 3 years from the initiation of protocol treatment for the monitoring of unexpected later developing toxicities or other morbidity and to document disease progression and survival. Data should be updated quarterly in the PBTC RDC database.

For patients who are eligible for extended therapy (5.4.1) they will be followed during this additional period for dates of drug administration, adverse events that are possibly, probably or definitely related to study drug, laboratory results, date of disease progression, and date of last follow up and date of death. At the completion of the additional 13 courses of therapy the patient is considered to have completed protocol therapy and should be taken off treatment (per protocol section 5.5). At the completion of the appropriate follow up period (per protocol section 5.6), the patient should be considered off study.

5.6 Criteria for Removal from Study

The date and reason for the patient coming off study must be documented in the eCRF and the Operations and Biostatistics Center must be notified according to standard reporting guidelines (see sections 7, 5.6.2 and the Required Data and Timetable Submission from located on the 033 protocol webpage).

- 5.6.1 Patients will be considered Off Study for the following reasons:
 - Patient determined to be ineligible.
 - Parent, patient, or guardian withdraws consent for continued participation.
 - Patient death while on study. The IRB, Investigational Drug Branch (IDB), Study Chair and OBC must be notified as per section 7.
 - Patient has been followed for 3 years from the initiation of protocol treatment.

5.6.2 Off-Study Data Submission

No data will be collected documenting treatment or reporting events or disease status that occurs subsequent to the official "off study" date with the exception of adverse events with an attribution of possible, probable, or definite that occur after the "off study" date for agents being studied under a CTEP IND (see section 7).

6. DOSING DELAYS/DOSE MODIFICATIONS

The study chair must be notified of any proposed dose modifications. After consultation with the Study Chair, the site should follow the dose modification guidelines in this section.

6.1 Dose Modification for DLT during ABT-888 and Radiation

6.1.1 Non-Hematologic

For ABT-888-related non-hematologic DLTs during radiation therapy, ABT-888 will be withheld until the toxicity resolves to meet on study parameters (section 3.1.6), and the patient will restart ABT-888 at one dose level lower (see **Table 10**), if not already at Dose Level 0. Patients who experience a non-hematologic DLT on Dose Level 0 will complete radiation without ABT-888.

6.1.2 Hematologic

For ABT-888-related hematologic DLTs, ABT-888 will be withheld until criteria described below are met, and ABT-888 will be restarted at one dose level lower, if not already at Dose Level 0. If the same DLT is experienced at the lower dose level, then ABT-888 should be discontinued. If a different DLT is encountered, then the patient may restart ABT-888 at the next lower dose level, if not already at Dose Level 0.

In the event of hematological DLT, CBC should be checked twice weekly until recovery of ANC $\geq 1,000/\text{mm}^3$ and platelet $\geq 100,000/\text{mm}^3$. A patient who experiences any DLT despite being treated at Dose Level 0 will complete radiation therapy without ABT-888. Irradiation should be continued despite ABT-888-related DLT, unless there is a clinical contraindication.

- a. \geq Grade 3 thrombocytopenia: Platelet transfusion is permissible and strongly encouraged for patients with dose-limiting thrombocytopenia to minimize the risk of intra-tumoral hemorrhage. ABT-888 should not be restarted until platelet count has recovered to \geq 100,000/mm³ (transfusion independent). Radiation therapy should not be interrupted unless clinically indicated.
- b. Patients with grade 4 neutropenia may receive filgrastim (G-CSF) support only for documented infection and/or sepsis, and they should re-start ABT-888 at the next lower dose level without GCSF support. ABT-888 should not be restarted until the ANC is ≥1,000/mm³ for at least 48 hours without G-CSF support. Radiation therapy should not be interrupted unless clinically indicated.

Patients who experience ABT-888-related DLTs during irradiation will still receive ABT-888 during maintenance therapy, provided that they meet the criteria to start subsequent course of

therapy and all prior ABT-888-related toxicities have resolved to baseline.

6.2 Dose Modification for ABT-888 and TMZ during Maintenance

Dose modifying toxicities will be defined as any of the following events that are at least (possibly, probably, or definitely) attributable to ABT-888 and TMZ. Dose de-escalation during maintenance should occur if any of the following dose modifying toxicities are present:

6.2.1 Non-Hematologic Toxicity

- Any grade 4 non-hematologic toxicity
- Any grade 3 non-hematologic toxicity with the exception of:
 - \circ Grade 3 nausea and vomiting of < 5 days
 - Grade 3 elevation of transaminases that returns to levels meeting eligibility criteria within 7 days of study drug interruption and does not recur upon restarting drug.
 - Grade 3 fever or infection of fewer than 5 days in duration
 - Grade 3 hypophosphatemia, hypokalemia, hypocalcemia or hypomagnesemia responsive to oral supplementation
- Any grade 2 non-hematologic toxicity that persists for > 7 days and is considered medically significant or sufficiently intolerable by patients that requires treatment interruption

For any of the above non-hematologic toxicities during maintenance therapy, ABT-888 and TMZ will be withheld until the toxicity resolves to meet on study parameters (section 3.1.6), and the patient will restart ABT-888 and TMZ at the next lower dose level (see **Table 12**). Protocol therapy will be discontinued if a non-hematologic dose modifying toxicity occurs at dose level 0.

- 6.2.2 Hematological Toxicity
 - \geq Grade 3 thrombocytopenia
 - Grade 4 neutropenia
 - A delay of > 14 days in starting subsequent cycles of maintenance due to ANC < 1,000/mm³ and/or platelet < 100,000/mm³ (for example, a patient never experienced grade 3 thrombocytopenia, but his/her platelet count lingered between 50,000 to 100,000/ mm³ beyond 42 days after the start of the previous course of maintenance therapy)

For the hematologic toxicities outlined above that occur during maintenance therapy, ABT-888 and TMZ will be withheld until criteria described below are met, and ABT-888 and TMZ will be restarted at the next lower dose level (see **Table 12**). Protocol therapy will be discontinued if a hematologic dose-modifying toxicity occurs at dose level 0.

- a. \geq Grade 3 thrombocytopenia: Platelet transfusion is permissible and strongly encouraged for patients with dose-limiting thrombocytopenia to minimize risk of intra-tumoral hemorrhage. ABT-888 and TMZ should not be restarted until platelet count has recovered to \geq 100,000/mm³ (transfusion independent).
- b. Patients with grade 4 neutropenia may receive filgrastim (G-CSF) support only for documented infection and/or sepsis. ABT-888 and TMZ should not be restarted until the

ANC is \geq 1,000/mm³ and for at least 48 hours without G-CSF support. Patients should start the subsequent cycle at the next lower dose level, without G-CSF support.

Complete blood counts should be repeated twice weekly for any hematological toxicity described above until counts recover to meet criteria for starting subsequent course of maintenance therapy.

7. ADVERSE EVENTS: LIST AND REPORTING REQUIREMENTS

Adverse event (AE) monitoring and reporting is a routine part of every clinical trial. The following list of AEs (section 7.1) and the characteristics of an observed AE (section 7.2) will determine whether the event requires expedited reporting (via CTEP-AERS) **in addition** to routine reporting.

- Baseline Abnormalities Any baseline (pretreatment) abnormalities observed during the initial physical examination should be recorded in the PedBraTum database.
- Routine AE Recording

Only record adverse events grades 1 and 2 if the attribution is at least possibly related to ABT-888. Record all adverse events grades 3 through 4 and deaths (while on treatment or within 30 days of treatment), regardless of attribution on the electronic case report forms (PedBraTum RDC database).

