1. OBJECTIVES

1.1 Phase I Primary Objectives

- 1. To identify the maximum tolerated dose or recommended Phase II dose of ABT-888 which can be safely administered concurrently with radiation therapy, followed by maintenance therapy with ABT-888 and TMZ, in patients with newly diagnosed DIPG.
- 2. To study the plasma pharmacokinetics (PK) of ABT-888 during ABT-888 and radiation therapy.
- 3. To study the feasibility of intra-patient dose escalation of TMZ during maintenance therapy with ABT-888 and TMZ.
- 4. To describe the toxicities associated with administering ABT-888 and radiation therapy, followed by ABT-888 and TMZ, in patients with newly diagnosed DIPG.
- 5. To estimate the proportion of newly diagnosed DIPG patients treated on protocol that are determined to have experienced pseudoprogression.

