5.1.3.1 Intra-patient Dose Escalation of TMZ during Maintenance

In an effort to maximize the TMZ dose (and potentially the efficacy of the combination treatment) that can be administered with ABT-888 for each patient, **intra-patient dose escalation of TMZ will be studied only for patients with minimal toxicities, considered at least possible related, in each course.** These patients' TMZ dose will be escalated (per Table 12) to 175 mg/m²/day (Dose Level 2), and subsequently to 200 mg/m²/day of TMZ (Dose Level 3) if the toxicities observed after 1 course of protocol therapy at each dose level meet the defined criteria. In patients who are not eligible to dose escalate after course 1 due to greater than minimal toxicities, there will be no further attempts to escalate the dose of temozolomide. Patients eligible to dose escalate after course 1 but are not dose escalated due to site related issues may start dose escalation in a subsequent course provided they meet all criteria for dose escalation.

Dose escalation of TMZ is not allowed if any of the following conditions exist:

Hematological Toxicity

- > Grade 1 thrombocytopenia
- > Grade 2 neutropenia

Non-hematologic Toxicity

- Any grade 4 non-hematologic toxicity
- Any grade 3 non-hematologic toxicity with the exception of:
 - \circ Grade 3 nausea and vomiting of < 5 days
 - Grade 3 elevation of transaminases that returns to levels meeting eligibility criteria within 7 days of study drug interruption and does not recur upon restarting drug.
 - Grade 3 fever or infection of fewer than 5 days in duration
 - o Grade 3 hypophosphatemia, hypokalemia, hypocalcemia or
 - o hypomagnesemia responsive to oral supplementation
- Any grade 2 non-hematologic toxicity that persists for > 7 days and is considered medically significant or sufficiently intolerable by patients that requires treatment interruption.

Intra Patiant Dasa Escalati	Intra-Patient Dose Escalation of TMZ during Maintenance Therapy (Days 1-5 per 28 day cycle)								
Dose Level									
0	20 mg/m ² BID	135 mg/m ² /day							
1 (Starting Dose)	25 mg/m ² BID	135 mg/m ² /day							
2	25 mg/m ² BID	$175 \text{ mg/m}^2/\text{day}$							
3	25 mg/m ² BID	$200 \text{ mg/m}^2/\text{day}$							

Table 12

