7.4 Routine Adverse Event Reporting

All Adverse Events must be reported in routine study data submissions. AEs reported through CTEP-AERS must also be reported in routine study data submissions.

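### The rule for recording grade 1-2 adverse events names only ABT-888 and conflicts with Section 7.4, so low-grade events attributed to temozolomide alone may go unrecorded although they can decide temozolomide escalation

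*Combined protocol and SAP*

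**What the plan says.** Two rules govern what is recorded.

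- Section 7, routine recording: "Only record adverse events grades 1 and 2 if the attribution is at least possibly related to ABT-888". For higher grades: "Record all adverse events grades 3 through 4 and deaths (while on treatment or within 30 days of treatment), regardless of attribution". Both are instructions for the electronic case report form.
- Section 7.4: "All Adverse Events must be reported in routine study data submissions". It sets no limit by grade or attribution.

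Two sections turn toxicity into action during maintenance.

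- Section 5.1.3.1 allows TMZ escalation only in "patients with minimal toxicities, considered at least possible related, in each course", without saying related to which agent. Its list of bars includes thrombocytopenia above grade 1 and "Any grade 2 non-hematologic toxicity that persists for > 7 days and is considered medically significant" (or intolerable enough to need treatment interruption).
- Section 6.2 defines dose-modifying toxicity as listed events "at least (possibly, probably, or definitely) attributable to ABT-888 and TMZ". The list repeats the persistent grade 2 non-hematologic criterion.

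Sections 5.1.3.1 and 13.1.3 halt escalation to a dose level when 2 of the first 2 to 6 patients, or 4 of the first 12, have dose-modifying toxicity. Section 13.1.3 limits the formal count to the first course at that level and adds periodic monitoring of later courses.

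The feasibility of TMZ escalation is primary objective 3 of Phase I (Section 1.1) and primary objective 2 of Phase II (Section 1.2). Phase I primary objective 4 is "To describe the toxicities associated with administering ABT-888 and radiation therapy, followed by ABT-888 and TMZ".

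**The concern.** The drug being escalated is TMZ, but the filter on low-grade events asks only about ABT-888. An event can therefore be severe enough to stop a patient's escalation and still fall outside what Section 7 lets the site record. Section 7.4 points the other way, so sites have two current instructions and may follow different ones.

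What is at stake is the trial-level use of the data: central application of the halting rule, the later-course monitoring promised in Section 13.1.3, the feasibility analysis, and the description of the regimen's toxicity. Attribution to TMZ alone is plausible: Table 14 in Section 7.1.2 lists its known toxicities, with nausea, constipation, anorexia and diarrhea in the likely column. The overall survival analysis is not touched.

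**Working it through.** The plan states no figure on this point, so there is nothing to reproduce. The check is to follow events below grade 3 through the sections.

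**Step 1. The persistent grade 2 non-hematologic event, by attribution**

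| Judged at least possibly related to | Recorded under Section 7 | Reported under 7.4 | Bars escalation (5.1.3.1) | Dose-modifying if 6.2 means either drug | Dose-modifying if 6.2 means both jointly |
|---|---|---|---|---|---|
| ABT-888 only | yes | yes | yes | yes | no |
| ABT-888 and TMZ | yes | yes | yes | yes | yes |
| TMZ only | **no** | yes | yes | yes | no |

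The gap is the third row. There Sections 7 and 7.4 disagree, and the event bars escalation on either reading of 6.2. Whether it also enters the halting count depends on how the word joining the two drugs in 6.2 is read, and the protocol does not settle that.

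**Step 2. Other criteria that can be met below grade 3**

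- Thrombocytopenia of grade 2 bars escalation under 5.1.3.1. It is not dose-modifying: Section 6.2.2 starts at grade 3, so the halting rule does not count it. Section 10 (Tables 18 and 19, footnote 1) requires weekly blood counts in all courses, so the value exists whether or not an adverse event is entered.
- A delay of more than 14 days for count recovery is dose-modifying under 6.2.2, whose own example is a patient who never reached grade 3 thrombocytopenia. It should be visible from course dates and blood counts.

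The exposure therefore centers on the one event in Step 1, plus the general description of low-grade toxicity.

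**Step 3. How little it takes to change a halting count**

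Suppose exactly 2 of the first 6 patients have a dose-modifying toxicity in their first course at a level, and one of these is the third-row event under the either-drug reading. A count from the case report form gives 2 − 1 = 1, below the threshold of 2. At 12 patients with 4 events, it gives 4 − 1 = 3, below 4. One unrecorded event is enough when the true count sits exactly on the threshold. How often that would happen is unknown.

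**Step 4. Other routes to the center**

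Section 6 requires the study chair to be told of any proposed dose modification. Under the either-drug reading, that is a second route for the third-row event. Under the joint reading the event is not dose-modifying, so the halting count loses nothing. It still bars escalation, though, and Section 6 does not clearly require notice when a patient is simply not escalated.

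**The case against.** The strongest reply is that the gap is small and partly closed already.

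- Both drugs are given on days 1-5, with ABT-888 60-120 minutes before TMZ (Section 5.1.3), and ABT-888 is there to enhance TMZ's effect (Section 2.3.2). Section 7.2 calls an event possible if it may be related to the study treatment as a whole. Many low-grade events would pass the ABT-888 filter. This stands and narrows the exposure, but it relies on investigators' judgment, and Section 7 asks specifically about ABT-888.
- Restricting low-grade capture to the investigational agent looks deliberate: Section 5.5.2 also follows toxicities to resolution only if related to ABT-888. That is reasonable for a commercial partner drug given at a fixed dose. It fits less well when that drug's escalation is itself a primary objective.
- Sites decide escalation from history, examination, laboratory results and the patient diary, not from the database. This stands. Individual decisions do not depend on the adverse event record.

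A reader might go further and infer that TMZ-related events are missing from the database, that halting counts are too low, or that the reason for withholding escalation cannot be verified. The documents do not support any of these. Section 7.4 requires all events, so what is shown is a conflict, not a loss. Most dose-modifying criteria are grade 3-4 and are recorded regardless of attribution. Weekly blood counts, visits before courses 2-10, diaries and notice to the study chair leave other evidence, although the documents do not clearly say that all of it enters the database.

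**Conclusion.** The point holds in narrow form. Sections 7 and 7.4 give conflicting recording instructions, and Section 7 does not match the attribution basis of Sections 5.1.3.1 and 6.2. Grade 1-2 events attributed to TMZ and judged unlikely or unrelated to ABT-888 may go unrecorded, including a persistent grade 2 event that bars escalation and, on one reading of 6.2, counts toward halting. The consequence is weaker support for Phase I primary objectives 3 and 4 and Phase II primary objective 2.

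The size cannot be derived. It would need the rate of such events and the share attributed to TMZ alone, and the documents give neither, so no percentage is offered. The conclusion assumes that at least some sites would follow Section 7 rather than 7.4, which is plausible because Section 7 is the more specific rule and names the case report form. This is an inexpensive improvement to data capture, not a flaw in the efficacy design.

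**What to change.** Amend the recording sentence in Section 7 so that, at least during maintenance, grade 1-2 events at least possibly related to ABT-888 or temozolomide are entered on the eCRF, and align Section 7.4 with it so that sites have one rule. State in Section 6.2 whether attribution to either drug or to both is meant, so that the halting count in Section 13.1.3 has one definition; which reading is intended is for the study team. No dose or escalation criterion needs to change for the recording fix.

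The cost is a small text change and slightly more data entry. If patients are already in maintenance when the change takes effect, the team would also need to decide whether to back-fill earlier courses from diaries and clinic notes.

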7.1 Comprehensive Adverse Events and Potential Risks List (CAEPR)

The Comprehensive Adverse Event and Potential Risks list (CAEPR) provides a single list of reported and/or potential adverse events (AE) associated with an agent using a uniform presentation of events by body system. In addition to the comprehensive list, a subset of AEs, the Specific Protocol Exceptions to Expedited Reporting (SPEER), appears in a separate column and is identified with *bold* and *italicized* text. The SPEER is a list of events that are protocol-specific exceptions to expedited reporting to NCI via CTEP-AERS (except as noted below). Refer to the 'CTEP, NCI Guidelines: Adverse Event Reporting Requirements' http://ctep.cancer.gov/protocolDevelopment/electronic_applications/adverse_events.htm for further clarification.

NOTE: The highest grade currently reported is noted in parentheses next to the AE in the SPEER. Report ONLY AEs higher than this grade expeditiously via CTEP-AERS. If this CAEPR is part of a combination protocol using multiple investigational agents and has an AE listed on different SPEERs, use the lower of the grades to determine if expedited reporting is required.

7.1.2 Adverse Event List for Temozolomide

Table 14							
Known Toxicities of Temozolomide							
Likely ($\geq 20\%$)Less Likely ($\leq 20\%$)Rare but Serious (<5%)							
Immediate: within 1-2 days of receiving drug	Anorexia Constipation Nausea Diarrhea	,Abdominal pain, Headache, Itching, Rash, Urinary frequency and/or infection, Vomiting, Dizziness, Anxiety, Confusion	Ataxia, Convulsions, Dysphagia, Hemiparesis, Thromboembolism				

Table 14
ovigities of Tomozol

NCI Protocol #: PBTC-033 Version Date: February 4, 2014 Updated Date: February 4, 2014

Prompt: Within 2-3 weeks, prior to next course	Myelosuppression	Lethargy, Mucositis, Peripheral edema; Fever (associated with low neutrophil count), Weight gain, Back pain, Breast pain, peripheral neuropathy, Upper respiratory infection, cough, sore throat, Myalgia, Amnesia, Depression, Visual changes, Insomnia	Myelosuppression for prolonged period with increased risk of infection or death; Hepatic failure
Delayed: Anytime later during therapy, excluding the above conditions		Alopecia	Hepatotoxicity
Late: Any time after completion of therapy			Secondary tumors or cancers

7.2 Adverse Event Characteristics

• **CTCAE term (AE description) and grade:** The descriptions and grading scales found in the revised NCI Common Terminology Criteria for Adverse Events (CTCAE) version 4.0 will be utilized for AE reporting. All appropriate treatment areas should have access to a copy of the CTCAE version 4.0. A copy of the CTCAE version 4.0 can be downloaded from the CTEP web site http://ctep.cancer.gov/protocolDevelopment/electronic applications/ctc.htm.

• For expedited reporting purposes only:

AEs for the investigational agent that are bold and italicized in the CAEPR (i.e., those listed in the SPEER column, section 7.1.1) should be reported through CTEP-AERS only if the grade is above the grade provided in the SPEER.

- **Attribution** of the AE:
 - Definite The AE is clearly related to the study treatment.
 - Probable The AE is likely related to the study treatment.
 - Possible The AE may be related to the study treatment.
 - Unlikely The AE is doubtfully related to the study treatment.
 - Unrelated The AE is clearly NOT related to the study treatment.

